Study Protocol and Statistical Analysis Plan

Official Title: Novel Management of Airway Protection in Parkinson's disease: A clinical trial

NCT number: NCT02927691

Document Date: (Grant submission – February 2016)

Study Protocol

This prospective experimental study will include two participant groups; one group will receive EMST and the other smTAP. Briefly, once enrolled in the study, participants will undergo baseline testing consisting of airway protective measures, physiological measures of respiratory and laryngeal function, and patient-centered outcome measures. Participants will then be randomly assigned with allocation concealment to either the EMST or smTAP training groups. They will be further randomized to receive immediate training or delayed training where there is a 5-week wait to start with a second baseline performed at the end of the 5-week delay. Whether participants are in the immediate or delayed start groups, once treatment commences they will receive 5 weeks of intensive training including weekly meetings with a treating clinician in our clinical-research laboratory. Upon completion of the treatment arm, participants will return for a post-treatment assessment consisting of all tests and measures from the initial baseline assessment. All treatment and assessment visits will be completed 'on' optimal PD medication dosage which will be defined as one hour after medication administration. Participants may use diet and/or postural modifications as recommended by their treating Speech-Language Pathologist to maintain nutritional status and swallowing safety during enrollment in the study, but are not to participate in other dysphagia exercise-based rehabilitation including treatments such as the effortful swallow, mendelsohn maneuver, etc. that have been shown to have exercise training effects (e.g., [10]). Pre- and post-treatment procedures are described below. More specific information about the selected outcomes is included in the 'clinical protocol synopsis'.

Pre and Post Treatment Assessments

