Swallowing Assessment Procedures. Three 10 cc thin liquid boluses by spoon and three 3-oz thin liquid sequential swallow challenges will be administered by cup. Our research team has extensive experience in the evaluation and measurement of swallowing dysfunction in PD (e.g., [20, 30, 31]). A recent retrospective analysis by our group of the swallowing performance of 50 participants with PD demonstrated that the 3-oz sequential swallow presentation was the best bolus presentation to detect change in swallowing performance. We will also include a smaller bolus (10 cc.) in the case that swallowing performance is so severe that it precludes the ethical presentation of the 3-oz liquid challenge.

Reflex Cough Assessment Procedures. Participants will be outfitted with a facemask covering the nose and mouth. The facemask will be coupled to a pneumotachograph, differential pressure transducer, and have a side port with a one-way inspiratory valve for nebulizer connection. The nebulizer will be a DeVilbuss T-piece connected to a dosimeter that delivers aerosolized solution during inspiration with a delivery duration of two seconds. The cough airflow signal will be digitized (Power Lab Data Acquisition System) and recorded (LabChart 7; ADInstruments, Inc) to a laptop computer.

Participants will be seated for an initial 30 seconds of quiet breathing in order to acclimate to the facemask. Participants will then complete a capsaicin challenge with three randomized blocks of 0, 50, 100, 200, and 500 μ M capsaicin dissolved in a vehicle solution. Our preliminary data identified 500 μ M as a supra-threshold concentration for eliciting the reflex cough in participants with PD. Participants will be given the instruction "cough if you need to" prior to capsaicin delivery. The solution will be administered automatically upon detection of an inspired breath and there will be a minimum of one minute between each trial. Participants will be provided water to drink between trials. Our research group has extensive experience utilizing this methodology to induce cough (e.g., [8, 22, 32, 33]). Our group holds an FDA IND # 76866 for the use of capsaicin in the study of cough reflex sensitivity and motor pattern.

Treatment protocols:

Every effort was made to match the two targeted treatments on amount of time with clinicians, home practice time, and number of repetitions.

Expiratory Muscle Strength Training (EMST)

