their performance on the first five coughs trained within each session in order to reduce the influence of clinician bias on treatment outcomes.

Home practice: The daily training sessions will be completed at home, with the assistance of the participant's primary caregiver if necessary. Each day approximately 20-30 minutes will be spent training. Home practice will be completed 5 out of 7 days. Participants will complete 25 voluntary coughs (5 sets of 5 repetitions) using a peak flow meter [36]. Each week the target peak cough flow will be 25% above maximum PEFR as identified during the study treatment visits to the laboratory.

Statistical Analyses

Multilevel models with main effects of treatment, time, and their two-way interaction will be used. A randomeffect of participant will be used to include multiple trials (eg, three trials of MEP at each time point). In the presence of an interaction, differences in the magnitude of change between groups, as well as changes within each group, will be examined. For primary outcomes, separate models will be performed for delayed to pre-training and pre-training to post-training cohorts. More specifically, for participants randomized to the delayed treatment group, MEP and voluntary cough PEFR will be tested between delayed (first baseline) and pre-training (second baseline). For the active treatment phase, all outcomes will be tested between pre-training. α will be set at 0.05, and multiple pairwise comparisons were adjusted via Holm–Bonferroni corrections. Standardized effect sizes will be computed by dividing mean difference by the error and random effect variance. Single measure, absolute agreement intraclass correlation coefficients and weighted Cohen's kappa will be used for cough airflow and number of coughs, respectively, for reliability. Analyses will be performed in R.

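### Individual MEP trials enter the model with participant as the only random effect, so tests of change are anti-conservative whenever participants vary from visit to visit

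*Combined protocol and SAP*

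**What the plan says.** All of the following is in the Statistical Analyses section unless another section is named.

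- Fixed effects: "Multilevel models with main effects of treatment, time, and their two-way interaction will be used".
- Repeat trials: "A randomeffect of participant will be used to include multiple trials (eg, three trials of MEP at each time point".
- Time points: for primary outcomes, "separate models will be performed for delayed to pre-training and pre-training to post-training cohorts", so each model compares two visits. In the delay phase, "MEP and voluntary cough PEFR will be tested between delayed (first baseline) and pre-training (second baseline".
- Effect sizes: "Standardized effect sizes will be computed by dividing mean difference by the error and random effect variance".
- Alpha is 0.05, with Holm–Bonferroni adjustment of pairwise comparisons.

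The section does not use the word intercept. It states no random slope, participant-by-time effect, residual covariance structure, averaging of trials, robust standard error or degrees-of-freedom method.

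Two other places bear on the point. The Study Protocol section partly standardises the visits, which all take place on "optimal PD medication dosage which will be defined as one hour after medication administration". The Reflex Cough Assessment Procedures section describes "three randomized blocks of 0, 50, 100, 200, and 500" μM capsaicin, which is 3 × 5 = 15 challenges per assessment.

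**The concern.** Treatment-by-time compares the changes of participants in one arm with those in the other. A participant intercept correlates all trials of one person, but it cancels when that person's two visits are subtracted. What remains is how much that person truly changed, anything specific to the visit such as effort or fatigue, and trial noise. Only the trial noise averages out over three blows. An intercept-only model puts all three in one residual and treats most of the participant-by-visit variance as if it averaged out too.

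The standard error is then too small, the interval too narrow and, by default, the degrees of freedom too large. The follow-up tests of change within each arm use the same residual. Holm–Bonferroni takes the p-values as given and does not repair them. Timing visits to medication limits one source of visit-to-visit variation, but not the others.

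**Working it through.** **Inputs.** From the Statistical Analyses section: m = 3 MEP trials per visit, 2 visits per model, alpha 0.05. Assumed: two-sided testing, equal arms, complete data, and r = Vc/Ve, where Vc is the participant-by-visit variance and Ve the trial variance. The documents give no variance component and no sample size, so there is no figure of the plan's own to reproduce.

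**True variance.** A participant's mean change has variance 2(Vc + Ve/3) = (2/3)(Ve + 3Vc).

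**Variance the model uses.** The intercept-only model uses (2/3)s². In large samples each participant contributes to s² about 4 degrees of freedom from trials within visits, with expectation Ve, and 1 from the change itself, with expectation Ve + 3Vc. Hence E[s²] = (4Ve + Ve + 3Vc)/5 = Ve + 0.6Vc.

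**Ratio.** True/model variance = (1 + 3r)/(1 + 0.6r), which exceeds 1 for every r > 0. The type I error is 2[1 − Φ(1.96/√ratio)]. For r = 0.5: 2.5/1.3 = 1.923, √1.923 = 1.387, 1.96/1.387 = 1.413, giving 15.8%.

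The second column gives the SD of participants' underlying changes, √(2r), in trial SDs. The last two columns are simulated treatment-by-time and within-group tests (20 per arm assumed, 20,000 runs).

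| r | SD of change | Variance ratio | SE too small by | Type I error | Simulated, interaction | Simulated, within group |
|---|---|---|---|---|---|---|
| 0 | 0 | 1.00 | 1.00 | 5.0% | 5.1% | 5.1% |
| 0.1 | 0.45 | 1.23 | 1.11 | 7.7% | 8.0% | 7.9% |
| 0.25 | 0.71 | 1.52 | 1.23 | 11.2% | 11.6% | 11.4% |
| 0.5 | 1.00 | 1.92 | 1.39 | 15.8% | 16.1% | 16.1% |
| 1 | 1.41 | 2.50 | 1.58 | 21.5% | 21.6% | 21.8% |
| 2 | 2.00 | 3.18 | 1.78 | 27.2% | 27.5% | 27.5% |

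As r grows the ratio tends to 5 and the type I error to 38%. Results at 30 per arm were nearly the same, so sample size does not cure the problem. Analysing visit means gave 4.8–5.3% throughout.

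**Check against fitted models.** In 240 REML fits (25 per arm assumed) the fitted standard error agreed with the closed form to four decimals. A separate run of 300 fits per setting (30 per arm) rejected in 3.7%, 11.7% and 22.7% at r = 0, 0.5 and 1. That run is noisy (Monte Carlo SE about 1–2 percentage points) but shows the same direction.

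**Degrees of freedom.** With 60 participants (assumed), the intercept-only residual has 4 × 60 + 58 = 298. The contrast of participants' changes has 60 − 2 = 58.

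**Other outcomes.** For m trials per visit the ratio is (1 + mr)/(1 + mr/(2m − 1)), so nothing is inflated at m = 1. For r from 0.1 to 2 the type I error is 6–18% at m = 2 and 10–39% at m = 5. Voluntary cough PEFR is affected only if more than one trial per visit is modelled; that number is not given.

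Capsaicin outcomes differ. If all 15 challenges were pooled with no concentration term, concentration would inflate the residual as well. Let q be the within-visit mean square it adds, divided by Ve. The test is anti-conservative if q < 15r and conservative if q > 15r. At r = 0.25 the type I error is 34%, 12%, 4.5% and 0.3% for q = 0, 2, 4 and 10.

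**The case against.** The algebra is hard to dispute; the reading and the size are open to challenge.

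- **Reading.** The plan gives no model formula. A random effect of participant could include a slope for time, and with two visits that would absorb the missing variance. The effect-size sentence does not count components and could cover several. This stands as a possibility, but it is strained: one random effect is named, its stated job is to accommodate repeat trials, and an analyst coding from the text would write (1 | participant). If a slope was meant, the plan still has to say so.
- **Size.** Nothing in the documents locates r, and at small r the inflation is modest (6.4% at r = 0.05). This stands in full. But r = 0 requires everyone in an arm to have the same true change over five weeks of training, with no shared visit effect.
- **Delay phase.** Differences in training response cannot operate before training starts, so r may be smaller there. This also stands. The formula is the same, but the upper rows of assumed r are less plausible for that model.
- **Other outcomes and degrees of freedom.** The plan does not say that capsaicin challenges are pooled, gives no trial count for voluntary cough PEFR, and names no degrees-of-freedom method. It refers to a clinical protocol synopsis that may hold some of this. Those figures are therefore conditional, and the point rests on MEP.

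**Conclusion.** The concern holds. Under the natural reading, the MEP treatment-by-time and within-group change tests are anti-conservative for every r > 0. The direction is certain. The size is not: about 8% to 27% against a nominal 5% for assumed r from 0.1 to 2, with standard errors too small by a factor of 1.11 to 1.78. These figures assume balanced data and two-sided tests. Because MEP is one of the two measures named for the primary-outcome models, the stated 0.05 is not assured for a primary measure. This should be corrected before analysis. The statements about voluntary cough PEFR and capsaicin outcomes depend on modelling choices that the plan does not state.

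**What to change.** For MEP, and for any other outcome whose repeat trials enter individually, specify a participant-by-time random effect in both the delay-phase and training-phase models: in R, (1 | participant) + (1 | participant:time). Alternatively, analyse one mean per participant per visit. In balanced data the two give the same test, on the number of participants minus two degrees of freedom.

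Secondary items:
- name Satterthwaite or Kenward–Roger degrees of freedom;
- state how many trials per visit enter the model for each outcome;
- for capsaicin outcomes, include concentration as a fixed effect or analyse by concentration;
- name the added variance component in the effect-size definition.

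The main change costs one line of SAP wording and model code and needs no new data. The secondary items add a few sentences. The price is wider confidence intervals, which is the uncertainty the present model would leave out.

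### Start time is randomised (immediate versus 5-week delay), but the analysis never compares the start groups, so any reading of change as benefit over no training would be uncontrolled

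*Combined protocol and SAP*

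**What the plan says.** The Study Protocol section of the combined document sets up two randomised factors. The first is EMST versus smTAP. For the second, participants are "further randomized to receive immediate training or delayed training where there is a 5-week wait to start with a second baseline" at its end. Once training begins, "they will receive 5 weeks of intensive training including weekly meetings with a treating clinician in our clinical-research laboratory", after which "participants will return for a post-treatment assessment consisting of all tests and measures from the initial baseline assessment". The section does not list what the second baseline measures.

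The Statistical Analyses section gives the model: "Multilevel models with main effects of treatment, time, and their two-way interaction will be used". Treatment is not defined there; read with the Study Protocol section, it means EMST versus smTAP. On follow-up tests: "In the presence of an interaction, differences in the magnitude of change between groups, as well as changes within each group, will be examined".

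The plan then splits its main endpoints by phase: "separate models will be performed for delayed to pre-training and pre-training to post-training cohorts". In the delayed group, "MEP and voluntary cough PEFR will be tested between delayed (first baseline) and pre-training (second baseline". This split is stated for the primary outcomes, while the training phase covers all outcomes. The sentence on the training phase breaks off before naming the second time point, which is evidently post-training. No start-group term and no comparison of immediate with delayed starters is stated.

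**The concern.** Randomising start time creates a concurrent group that has not yet been trained. The stated analysis gives up that advantage by splitting the data by phase. One model looks at change during the wait in delayed starters, another at change during training, and the two are not compared. A significant training-phase change next to a non-significant delay-phase change does not show that the changes differ.

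The point bites if EMST and smTAP improve alike, which is plausible because the protocol says every effort was made to match them on clinician time, home practice and repetitions. There would then be no interaction. The plan ties within-group change to the presence of an interaction, so what remains is a time effect, and the plan does not say how it will be read. Retest effects, regression to the mean or the passage of time could each contribute to it. If it were presented as benefit over no training, it would rest on an uncontrolled before-after comparison although a randomised one was available.

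**Working it through.** **Step 1: does the randomised comparison exist?**

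| | Enrolment | About week 5 |
|---|---|---|
| Immediate start | Baseline | Post-treatment assessment, after 5 weeks of training |
| Delayed start | First baseline | Second baseline, after a 5-week wait |

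Both intervals are about 5 weeks from enrolment and the groups were formed by randomisation. The comparison exists for MEP and voluntary cough PEFR, because the plan's delay-phase test needs both at the second baseline. For other outcomes it depends on what that visit measures.

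**Step 2: is it used?** The stated terms are treatment, time and their interaction. The delay-phase model contains delayed starters only. The training-phase model sets each person's pre-training value against post-training. Neither compares start groups over the same calendar interval.

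**Step 3: how much reassurance would the delay-phase test give?** The documents give no sample size, SD, drift or allocation ratio, so there is no figure to reproduce and what follows is illustration. Assumptions: two-sided alpha 0.05, SD of visit-level change 1, half of participants delayed, no training effect, drift g in the direction of improvement. No Holm correction is modelled.

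A one-sample t test of change in n people has noncentrality g × √n on n − 1 degrees of freedom.

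- Delay-phase test, 30 delayed, g = 0.3: 0.3 × √30 = 1.64, power 0.355.
- Training-phase time effect, N = 60, same drift in that interval: 0.3 × √60 = 2.32, rejection probability 0.628.

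Power of the delay-phase test to detect drift:

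| Delayed participants | g = 0.2 | g = 0.3 | g = 0.4 |
|---|---|---|---|
| 20 | 0.136 | 0.247 | 0.397 |
| 30 | 0.185 | 0.355 | 0.563 |
| 40 | 0.235 | 0.457 | 0.694 |

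The 0.628 depends on how drift behaves. By simulation at N = 60 and g = 0.3, it falls to 0.41 if drift is halved in the later interval and to 0.20 if drift occurs only at the first retest. Across these patterns the immediate-versus-delayed contrast stays at about 0.05, because drift over the first 5 weeks is common to both groups.

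**Step 4: what precision would the randomised contrast have?** At an assumed N of 60 there are 15 immediate starters per training arm and 30 delayed.

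- One arm versus all delayed: SE = √(1/15 + 1/30) = 0.316. The 95% CI half-width is 2.017 × 0.316 = 0.64 SD. Power for 0.5 / 0.8 SD is 0.34 / 0.70 before Holm.
- Pooled, 30 versus 30: SE = √(2/30) = 0.258. The half-width is 2.002 × 0.258 = 0.52 SD. Power is 0.48 / 0.86 if both arms gain that much.
- Before-after mean, all 60: half-width 2.001 / √60 = 0.26 SD.

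**Step 5: pooled or by arm?** If one arm gains 0.8 SD and the other nothing, the pooled effect is (0.8 + 0) / 2 = 0.4 SD. Pooled power at N = 60 is then about 30%, against about 70% for the effective arm versus all delayed.

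**The case against.** The strongest reply is that the plan is being faulted for a claim it does not make. The trial compares two active trainings, that contrast is randomised, and the supplied text states no aim of showing benefit over no training. This stands, and it limits the point to how time effects and within-arm changes may be read. The Study Protocol section also refers to a clinical protocol synopsis that is not supplied, so an aim or contrast stated there cannot be checked.

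Second, the delay-phase test is introduced for the primary outcomes, and MEP and voluntary cough PEFR read as those outcomes. Limiting a control-phase check to primary outcomes is a normal choice, so its two-outcome scope is not the main weakness. What remains is that it is a before-after test in one start group and is not compared with training-phase change.

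Third, the illustration rests on assumed drift. Only drift towards improvement would mimic benefit; decline would work against such a claim. Regression to the mean needs selection on extreme values, and the supplied text gives no eligibility criteria. This also stands: the figures show the behaviour of the tests, not a predicted bias.

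A reader might infer that the missing contrast undermines the EMST-versus-smTAP result. The documents do not support that: both arms share the same schedule and the treatment-by-time contrast is randomised. A reader might also add the effect of a participant-only random effect with three trials per visit on type I error. That is a separate issue about model structure and adds no weight here.

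**Conclusion.** The point holds in a limited form and should be fixed. It is certain from the text that start time is randomised and that no immediate-versus-delayed comparison is stated in the supplied document. The consequence is conditional: it arises only if a time effect or within-arm change is read as benefit over no training. In that case the inference would be uncontrolled, and a non-significant delay-phase test would be weak evidence against drift, with power of roughly 14% to 69% for 20 to 40 delayed participants and drift of 0.2 to 0.4 SD of change. Sample size, allocation, SD and the size and direction of drift are all assumptions. It does not follow that the plan makes an unsupported efficacy claim.

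**What to change.** Keep the planned EMST-versus-smTAP comparison. Add a baseline-to-week-5 analysis of all randomised participants for MEP and voluntary cough PEFR, and for any other outcome measured at the second baseline; list those outcomes in the SAP.

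- Compare change in immediate EMST versus delayed and in immediate smTAP versus delayed, adjusted for the baseline value, with 95% CIs. Use visit means or a participant-by-visit random effect.
- Base any claim of benefit over no training on these two arm-specific contrasts, with Holm correction across the two. Report a pooled contrast only as supportive: EMST is loaded on MEP and smTAP targets cough PEFR, so pooling averages unlike effects and could credit an ineffective arm.
- State that the contrast compares training plus weekly clinician contact with waiting.
- Label within-arm, time-main-effect and delay-only changes descriptive.

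The cost is SAP wording and one extra model per outcome, with no new visits for MEP and voluntary cough PEFR. The price is precision: at an assumed N of 60, a half-width of 0.64 SD by arm against 0.26 SD for the before-after mean, and power of about 34% / 70% for 0.5 / 0.8 SD before Holm. These figures take no credit for baseline adjustment, which may recover some precision. The contrasts are therefore added to the planned models and do not replace them.

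### Does the lack of a success rule and a defined Holm family for the primary outcomes inflate the trial's type I error?

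*Combined protocol and SAP*

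**What the plan says.** The Statistical Analyses section uses the plural without a count: "For primary outcomes, separate models will be performed for delayed to pre-training and pre-training to post-training cohorts". The next sentence, on participants randomized to delayed treatment, says that "MEP and voluntary cough PEFR will be tested between delayed (first baseline) and pre-training (second baseline". That is the nearest the supplied text comes to naming the primary outcomes. For the training phase it says "For the active treatment phase, all outcomes will be tested between pre-training", with no ranking of outcomes; the sentence breaks off before the second time point, evidently post-training.

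On multiplicity there is one sentence: "α will be set at 0.05, and multiple pairwise comparisons were adjusted via Holm–Bonferroni corrections". The comparisons it most naturally refers to are the follow-ups described earlier in the section: "In the presence of an interaction, differences in the magnitude of change between groups, as well as changes within each group, will be examined".

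The opening Study Protocol section points elsewhere for detail: "More specific information about the selected outcomes is included in the 'clinical protocol synopsis". That synopsis is not in the supplied text. In the smTAP description PEFR is called a primary target, but that means a training target and does not declare an endpoint.

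**The concern.** With two primary outcomes and one alpha, a reader wants to know what counts as success. If a difference on either outcome is enough and each is tested at 0.05, the chance of at least one false positive exceeds 0.05. The Holm sentence does not plainly prevent this, because it is worded for pairwise comparisons and can be read as covering only the contrasts that follow a significant interaction.

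There is a further wrinkle. With two arms and two time points, the treatment-by-time interaction has one degree of freedom and is the same test as the between-group difference in change. The plan therefore lists one hypothesis twice: as the gate, apparently uncorrected, and as a follow-up, possibly corrected. Two analysts could report different p-values for the main comparison. The error rate of the primary conclusion, and possibly the conclusion itself, would then depend on a choice that the text leaves open.

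**Working it through.** **Inputs.** The only design figure in the documents is "α will be set at 0.05"; sidedness is not stated, and two-sided is assumed. Two primary outcomes is an inference. The documents give no correlation between the test statistics (rho), so 0 to 0.9 is assumed. They state no familywise error, power or sample size, so there is no figure of the plan's own to reproduce.

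**Either outcome suffices, no adjustment across outcomes.** For independent tests the error is 1 − (1 − 0.05)² = 1 − 0.9025 = 0.0975. For correlated tests it is P(|Z₁| > 1.96 or |Z₂| > 1.96) under a bivariate normal distribution.

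**Both required, no effect on either.** P(both) = 0.05 + 0.05 − P(either). If only one outcome has a true effect, the false joint claim is limited by the other outcome's test, so it never exceeds 5%.

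**Holm across the two.** With no effect on either, an error occurs when the smaller p-value falls below 0.025. For independent tests this is 1 − 0.975² = 0.0494.

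| Assumed rho | Either at 0.05 | Both at 0.05 | Holm across both |
|---|---|---|---|
| 0 | 9.75% | 0.25% | 4.94% |
| 0.3 | 9.51% | 0.49% | 4.84% |
| 0.5 | 9.07% | 0.93% | 4.65% |
| 0.7 | 8.35% | 1.65% | 4.30% |
| 0.9 | 7.04% | 2.96% | 3.62% |

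The 7.0% is not a lower bound. At rho 0.99 the either-suffices error is 5.7%, and it tends to 5% as rho approaches 1.

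**What must hold for the second column to apply.** All three of these: exactly two primaries, one overall claim that either can establish, and a Holm family that stops at the single model. The first is a reasonable inference. The supplied text says nothing for or against the second. On the third, "multiple pairwise comparisons were adjusted via Holm–Bonferroni corrections" fits the narrow reading at least as well as the wide one but does not exclude the wide one.

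**The doubled test.** A Holm-adjusted p-value is never smaller than the raw one. If the between-group difference in change is corrected after the gate, the result is more conservative than the gate alone. The duplication can cost power; it cannot add type I error.

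**What a forced split would cost.** Take a test with an assumed 80% power at 0.05, so a noncentrality of 1.960 + 0.842 = 2.802.

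- Power at 0.025 is Φ(2.802 − 2.241) = Φ(0.561) = 0.712.
- Regaining 80% at 0.025 needs a sample-size ratio of ((2.241 + 0.842)/(1.960 + 0.842))² = 1.21, about 21% more participants.
- With both effects true and independent tests, Holm power per outcome is 0.712 + (0.800 − 0.712) × 0.712 = 0.775. At rho 0.9 it is 75.1% if the effects share a direction and 80.0% if they are opposed.
- With only one effect true, power for it is about 71%.

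**The case for a change.** The best case for acting is that the rule decides what this trial concludes. EMST is set to 75% of MEP and smTAP trains toward a PEFR target, so a difference on one outcome only, or differences favouring different arms, is quite plausible. Whether that counts as success should not be settled after the data are seen. A few sentences would settle it, and if the sponsor already means Holm to span outcomes, saying so costs no power.

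Part of this stands. The supplied text contains neither a success rule nor a defined Holm family, and the conditional error rates are right.

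The same fact about the arms also cuts the other way. If one treatment may win on MEP and the other on PEFR, there is no obvious single claim for an either-or-both rule to govern. The natural report is one conclusion per outcome, and testing each at 0.05 is then an accepted convention. Declaring that either outcome may carry the trial would impose a claim that the plan does not make. Nor can the supplied text support a declaration that MEP and PEFR are the primaries and everything else is secondary: that could contradict the synopsis, and it would demote the swallowing and reflex cough outcomes on inference alone.

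**Conclusion.** The concern does not call for a change. It identifies an ambiguity, not a demonstrated excess of type I error. The excess is at most 4.75 percentage points (9.75% against 5%), for two independent tests. It shrinks to about 2.0 points at an assumed rho of 0.9 and vanishes if both outcomes are required or Holm spans them. It arises only under a success rule and a Holm scope that the supplied text does not establish, and the synopsis that it cites may already hold the rule.

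Analysts can fill the gap sensibly: report the treatment-by-time result for each outcome with its own p-value and keep the conclusions outcome-specific. A reader who prefers joint control can compare the smaller of the two p-values with 0.025 and, if it passes, the other with 0.05.

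Making that split mandatory would buy familywise control of a claim the plan does not state. The price is a fall from 80% to 71% power at the first step, or about 21% more participants to restore it. Whether to pay that in a comparison of two active treatments is a judgement on which statisticians may fairly differ. This conclusion assumes two primaries, two-sided tests, bivariate normal statistics and a hypothetical 80% power, since the documents give none.

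### The standardized effect size is defined with a variance in the denominator, so as written it depends on the unit of measurement; the square root should be stated (descriptive output only)

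*Combined protocol and SAP*

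**What the plan says.** The only specification of the effect size is one sentence in the Statistical Analyses section: "Standardized effect sizes will be computed by dividing mean difference by the error and random effect variance". The two variance components come from the models described at the start of that section: "Multilevel models with main effects of treatment, time, and their two-way interaction will be used", with a participant random effect to accommodate repeated trials at each time point. For the primary outcomes, the delay period and the training period are modelled separately.

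Inference is set out independently of the effect size: alpha "will be set at 0.05, and multiple pairwise comparisons were adjusted via Holm–Bonferroni corrections". The document contains no SD, no numerical effect size and no sample-size calculation. No test or decision rule uses the standardized effect size.

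**The concern.** A standardized effect size is meant to be free of units, which requires a denominator on the same scale as the numerator, that is, an SD. The sentence names a variance. It also does not say that the two components are to be added, so an analyst has to supply two steps: the sum and the square root.

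An analyst who adds the components and follows the rest literally would report a number labelled as a standardized effect that cannot be read as one. It would change with the unit in which the outcome was recorded. MEP is a pressure and PEFR a flow, so both have units that can be changed.

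The separate models add a smaller problem. The same outcome will have different estimated variances in the delay and training phases. If a reader sets the two effects side by side, the literal formula squares the ratio of the SDs.

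**Working it through.** There is no figure in the plan to reproduce, so the check is one of units and rescaling, followed by illustrations under stated assumptions.

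**Definitions.** Let D be the mean difference and S² = participant variance + residual variance.

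- As written, with the components summed: D / S²
- SD-based: d = D / S
- Hence the literal value = d / S

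**Rescaling (no assumptions needed).** Multiply the outcome by k. D becomes kD and S² becomes k²S². The literal value becomes kD / (k²S²) = (1/k) × D/S². The SD-based value becomes kD / (kS) = D/S, unchanged. The literal value matches d only if S = 1; it is too small when S > 1 and too large when S < 1.

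**MEP in cm H2O.** The EMST section gives a device range of 25 to 150 cm H2O and a setting of 75% of MEP. The MEPs the device can serve at that setting run from 25/0.75 = 33.3 to 150/0.75 = 200, a width of 166.7. Two assumed total SDs follow:

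- one sixth of the width: 166.7/6 = 27.8
- uniform over the width: 166.7/√12 = 48.1

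For d = 0.5 the literal value is 0.5/27.8 = 0.018 or 0.5/48.1 = 0.010, which is 28 to 48 times too small.

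**MEP with smaller assumed SDs.** Take D = 10 cm H2O, participant SD 15 and residual SD 10.

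- S² = 225 + 100 = 325 and S = 18.0
- literal: 10/325 = 0.031
- SD-based: 10/18.0 = 0.555
- the same data in kPa (factor 0.0980665): literal 0.314, SD-based still 0.555

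**PEFR.** The section does not state its unit. The total SDs of 0.9 to 1.9 L/s below are assumed.

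| Unit | Total SD | Literal value when d = 0.5 |
|---|---|---|
| L/s | 0.9 to 1.9 | 0.56 to 0.26 |
| L/min | 54 to 114 | 0.0093 to 0.0044 |

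In L/s the error can be small and can go in either direction. The change to L/min alone moves the literal value 60-fold.

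**Two phases.** Assume the same raw change D in both phases and total SDs of 25 and 30.

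- SD-based ratio: (D/25)/(D/30) = 30/25 = 1.20
- literal ratio: (D/625)/(D/900) = 900/625 = 1.44

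**The case against.** The strongest reply is that the sentence is shorthand. It calls the quantity standardized, names the sources of variance used for scaling and is not offered as a formula. Reading it literally means supplying the missing sum while withholding the missing square root. The document is dated as a grant submission, where compressed wording is common. This is probably what was meant. It lowers the chance that wrong numbers would be reported, but an analyst has only this sentence to work from.

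Second, nothing inferential depends on the effect size. This stands in full. Two arms compared within one model also keep their relative size, because they share a denominator.

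Third, every SD used above is assumed. The MEP range comes from the specification of a valve, not from the participants, and the smTAP group does not train on that device. The factor of 28 to 48 is also tied to the unit: in kPa the same SDs are about 2.7 to 4.7, so the factor is roughly 3 to 5. This is fair as to the exact size. It leaves the conclusion intact, since a total SD near 1 cm H2O is implausible and a factor that changes with the unit is itself the defect.

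Fourth, the plan does not call for comparing standardized effects between phases, or between MEP and PEFR, and the SD-based form also differs between phases. That is correct. The phase example shows only how the distortion grows if a reader makes the comparison.

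**Conclusion.** The concern holds. As written, the rule gives a quantity in units of 1/outcome, and no other part of the document corrects it. That conclusion follows from units alone and is firm.

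The numerical size is illustrative. For MEP in cm H2O the understatement is 28- to 48-fold under the two SDs derived from the device range, and 18-fold with the smaller assumed SDs. For PEFR in L/s it may be slight. The 60-fold dependence on L/s versus L/min needs no assumption about SDs.

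Severity is minor: only a descriptive output is affected, and the SD-based form was probably intended.

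**What to change.** In the Statistical Analyses section, replace the description of the denominator so that the effect size is defined as: *mean difference divided by the square root of the sum of the participant random-effect variance and the residual error variance, taken from the model for that outcome and phase*. The square root and the sum correct the defect. The closing words make explicit which variance components to use, given that the phases are modelled separately.

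The cost is one phrase. No new data are needed and no planned test changes, because the planned models already estimate both components.
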